## **6.1 PRIMARY ENDPOINT ANALYSIS**

The primary endpoint, defined as the clinical recurrence of AF or device-detected AF lasting longer than 30 seconds, will be analyzed as a time-to-event outcome. Follow-up time for participants who do not experience the primary endpoint will be censored at the time of study withdrawal or end of study (month 6). Kaplan-Meier plots will be used descriptively to compare the survival distributions of the primary endpoint by randomization arm. Cox proportional hazards regression models including the randomization assignment will be used to formally analyze the primary endpoint (AF recurrence). These models will also include study site, used in the randomization procedure as a stratification factor, and additionally baseline patient characteristics in sensitivity analyses. Point estimates and Wald-based 95% confidence intervals and p-values will be reported. The primary ITT analysis will include all participants regardless of compliance with randomized allocation.

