**Table 2. Schedule of Evaluations and Visits**

	Screening	Baseline	Follow-Up Phone Calls		
	Visits 1a-1b	Visit 1c	Visit 2	Visit 3	Visit 4
			Month 1	Month 3	Month 6
		Cardioversion			
Initial inclusion/exclusion evaluation	X				
Screen for coffee consumption habits	X				
Screen for significant other caffeinated product consumption	X				
Informed consent	X				
Demographics		X			
Height and weight		X			
Detailed history of coffee consumption habits		X	X	X	X
Detailed history of alcohol consumption habits		X	X	X	X
Detailed medical history		X	X	X	X
Targeted medication history		X	X	X	X
Assessment of clinically available pre-cardioversion ECG		X			
Assessment of clinically available post-cardioversion ECG		X			
Randomization		X			
Detailed history of other caffeinated product consumption			X	X	X
AF symptoms			X	X	X
Assessment of AliveCor KardiaMobile or Apple Watch ECG strip			X	X	X
Assessment of clinically available ECG or ambulatory			X	X	X

ECG monitoring from physician/healthcare provider					
Adverse events/serious adverse events evaluation			X	X	X
Targeted medical care utilization			X	X	X
Vital status			X	X	X

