### 5.7 Targeted Medication Inventory

Current/regular use (since the last study follow up) of a specific list of concomitant medications/therapies will be documented at baseline (post cardioversion) and at all follow-up visits. Medication data will be collected by self-report and electronic medical record on a CRF and will include type of medication. The list of targeted medications/therapies includes AF-related medications (e.g., anticoagulants, antiarrhythmics, negative chronotropic agents).

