## 10.0 STATISTICAL METHODS

### 10.1 Sample Size and Randomization

The goal of this trial is the enroll a total of 200 participants (n=100 per treatment group).

Assuming a 0.05 two-tailed alpha level, 1:1 randomization scheme, 50% recurrence rate in the absence of coffee, and potential 10% loss to follow-up, a sample size of n=200 (100 per arm) will provide approximately 80% power to detect a 1.63 times increased hazard of AF recurrence between the groups.

The table below summarizes the minimum detectable relative hazards in Cox models with binary predictor, by baseline AF recurrence rate (RR) (rows) and Percent Lost to Follow up (LTFU) (columns)

	5% LTFU	10% LTFU
50% RR	1.68	1.69
60% RR	1.62	1.63

Randomization will be performed 1:1 with stratification across sites.

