### **5.0 SAMPLE SIZE AND POWER CALCULATIONS**

The goal is to enroll a total of 200 participants (n=100 per treatment group) study-wide.

The sample size is based on the following assumptions: (1) a 50% incidence of AF recurrence; (2) 10% loss to follow-up; and (3) 0.05 two-tailed alpha level. Under these assumptions, a sample of 200 individuals randomized 1:1 to either coffee abstention or continued caffeinated coffee consumption will provide 80% power to detect a 1.63 times increased hazard of AF between the groups.

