### **6.0 STATISTICAL METHODS**

All analyses will be conducted upon completion of data collection and database lock. No interim analyses are planned.

The primary analysis will be by intention-to-treat (ITT), according to randomized allocation, without regard to participant compliance with this randomized allocation. Every attempt will be made to collect data for both primary and secondary endpoints until the end of the six month follow-up period for all randomized participants, and all data will be included as part of the primary ITT analysis.

Although substantial crossover is not anticipated, as treated and per protocol analyses will be conducted if failure to comply with the randomized allocation occurs in more than 10% of all participants or if there is a significantly different proportion of assignment adherence in one group compared to the other. The per protocol analyses will be restricted to a sub-sample excluding all the protocol violators, and adjust for any baseline factors that are imbalanced ( $P<0.1$ ) in the per-protocol sub-sample.

Patient baseline characteristics will be summarized overall and by randomization assignment. Continuous variables will be summarized using means and standard deviations (SD) for normally

distributed measures or medians and quartiles for non-normally distributed measures. Categorical variables will be summarized using contingency tables that display counts and percentages.

All tests will be two-sided with a 0.05-level of significance. Adjustment for multiple comparisons will not be used.

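### The primary Cox model is valid but adjusts for site only; a short prespecified list of baseline factors could add power at little cost, by an amount the documents do not determine

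*Combined protocol and SAP*

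**What the plan says.** **Model.** SAP 6.1 fits a Cox model with randomized arm and site. Other baseline factors enter as "additionally baseline patient characteristics in sensitivity analyses". None is named, and no coding or missing-value rule is given. SAP 6.2 treats the secondary endpoints the same way.

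**Data.** Protocol Table 2 schedules demographics, height and weight, coffee, alcohol and medical history, "Targeted medication history" and reading of the pre- and post-cardioversion ECGs at the baseline visit. Protocol 5.7 adds: "The list of targeted medications/therapies includes AF-related medications (e.g., anticoagulants, antiarrhythmics, negative chronotropic agents". Inclusion criterion 2 admits patients in AF or in flutter, so the entry rhythm can be read from the ECG.

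**Design.** SAP 5.0 states: "The goal is to enroll a total of 200 participants (n=100 per treatment group) study-wide". It assumes "a 50% incidence of AF recurrence", which Protocol 10.1 words as a "50% recurrence rate in the absence of coffee", together with 10% loss to follow-up, and claims "80% power to detect a 1.63 times increased hazard of AF between the groups". SAP 6.0 adds: "All tests will be two-sided with a 0.05-level of significance". The table in Protocol 10.1 is for a Cox model with one binary predictor, so the planning effect is an unadjusted hazard ratio (HR).

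Neither document says which baseline factors predict recurrence or how strongly, or why they are kept out of the primary model.

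**The concern.** The hazard ratio is non-collapsible. If factors that predict recurrence are left out of a Cox model, the estimated treatment HR is pulled toward 1 and the test loses power, even under perfect randomization. The trial is small and, on its own inputs, has no power to spare (see the working). The data are already scheduled and the adjusted model is already planned; only its status as a sensitivity analysis stops it from supporting the primary conclusion. At stake is some chance of detecting a real effect. The validity of the primary test is not in question.

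**Working it through.** **1. The plan's own figure.** Schoenfeld events for HR 1.63, 80% power and two-sided 0.05:

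D = 4(1.960 + 0.842)² / (ln 1.63)² = 31.4 / 0.2387 ≈ 132.

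Take 50% as the no-coffee arm, as Protocol 10.1 words it. The other arm then has 1 − 0.5^1.63 = 67.7%, so the mean is 58.8% and 200 participants give 117.7 events. If half of the 10% loss removes information, D = 117.7 × 0.95 = 111.8. Power = Φ(√111.8 × 0.4886/2 − 1.960) = Φ(0.62) ≈ 73%. With the 10% lost in full, D = 105.9 and power is 71%. If 50% is the overall rate, D = 90 and power is 64%.

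The stated 80% is therefore not reproduced at 50% recurrence. The half-loss method gives a minimum detectable HR of 1.69 at 50%/10%, matching that cell of the protocol's table. It gives 1.63 at 60%/10%, which is where the text's figure belongs. That mismatch is a separate point. Here it only sets the baseline: power of roughly 71–73%.

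**2. Simulation at the design effect.** Set-up: 100 per arm, three sites, exponential times, 50% recurrence in the reference arm, 10% uniform loss, about 113 events, Wald test, 3,000 runs per row. The unadjusted HR is held at about 1.63. Five baseline covariates form a prognostic score whose SD on the log-hazard scale is **assumed**. One SD multiplies the hazard by e^0.3 = 1.35, e^0.5 = 1.65 or e^0.75 = 2.12.

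| Score SD | Power, arm + site | Power, adjusted | Average HR, arm + site → adjusted | SE of log HR, arm + site → adjusted |
|---|---|---|---|---|
| 0 | 75.3% | 75.4% | 1.653 → 1.669 | 0.193 → 0.197 |
| 0.3 | 74.3% | 76.3% | 1.652 → 1.695 | 0.193 → 0.197 |
| 0.5 | 74.2% | 80.3% | 1.651 → 1.746 | 0.193 → 0.198 |
| 0.75 | 74.2% | 86.1% | 1.647 → 1.839 | 0.193 → 0.199 |

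The gains are 0, 2, 6 and 12 points, roughly what 0%, 5%, 16% and 36% more events would give. Ten covariates gave the same gains within simulation error.

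**3. Where the gain comes from.** Approximate power is Φ(ln HR / SE − 1.960). At SD 0.5:

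- arm + site: 0.5014/0.193 = 2.60, so Φ(0.64) ≈ 74%
- adjusted: 0.5573/0.198 = 2.81, so Φ(0.85) ≈ 80%

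The SE rises slightly. All of the gain is in the numerator.

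**4. Holding the conditional HR fixed instead.** At a conditional HR of 1.69 (about 112 events, five covariates), arm-plus-site against adjusted power was 79% vs 80% (SD 0), 76% vs 77% (0.3), 71% vs 78% (0.5) and 66% vs 79% (0.7): gains of 1, 1, 7 and 13 points. At a conditional HR of 1.63 it was 74% vs 75%, 70% vs 72%, 64% vs 71% and, at SD 0.75, 56% vs 71%. The last gap of 15 points is left out of the headline range because the unadjusted effect has by then fallen well below the planned 1.63.

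**5. Type I error.** The adjusted model gave 4.8–6.2% over SD 0 to 1.0, and arm plus site 4.2–5.8% (simulation SE about 0.5 points). This shows no material inflation, though a slight one cannot be excluded.

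**6. What missing covariates could cost.** With HR 1.63 and 113 events, power is Φ(10.63 × 0.2443 − 1.960) ≈ 74%. If incomplete records are dropped and 5% of events go with them (an assumption), 107.4 events give 72%; at 10%, 101.7 events give 69%. That cancels the gain at SD 0.3 and most of it at SD 0.5.

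**The case against.** The strongest reply is that nothing is wrong. Arm plus the stratification factor is a standard primary model, SAP 6.1 already plans the fuller one, and the proposal swaps two labels for a gain that the documents cannot size. This stands as to validity. It does not remove the reason for the swap, because a sensitivity analysis cannot carry the primary conclusion.

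Second, the adjusted HR is a different estimand. Site is in the model because randomization was stratified on it, so its presence does not make conditioning on clinical factors trivial. This stands as a cost. With no treatment effect both HRs equal 1, so the null hypothesis is unchanged, and keeping the arm-plus-site result preserves the other estimate.

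Third, practical risks. The SAP has no rule for missing baseline values, while 6.1 promises that every participant is in the primary ITT analysis. Protocol 5.7 dates the baseline medication record to after cardioversion, and SAP 4.1 randomizes as soon as possible after it; neither says which comes first. The trial is open-label, and SAP 2.0 describes randomization in the past tense, so a late change could look data-driven. All three stand, and the fix has to answer them.

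A reader might go further and infer that the plan is in error, that adjustment is free, that it improves precision, or that a sizeable loss of power is established. The documents support none of these. The primary model is valid, the costs above are real, the SE rises slightly, and no prognostic strength is given.

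**Conclusion.** An efficiency improvement worth making. Confidence is high for the direction and low for the size. Adjustment would add about 0–2 points of power if the listed factors are weak (SD 0–0.3) and about 6–13 points if they are moderate (SD 0.5–0.75). The range rests on those assumed strengths, on proportional hazards, on 50% recurrence in the no-coffee arm, and on all randomized participants staying in the model. The case for acting is asymmetric: uninformative covariates cost about nothing in the simulations, while moderately informative ones help materially. Adjustment should not be read as restoring the stated 80%, since whether it reaches that depends on the unknown strength.

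**What to change.** In SAP 6.1:

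- Define the primary ITT Cox model as arm, site and a short named list with coding, for example age, sex, BMI, heart failure history, entry rhythm (AF or flutter) and antiarrhythmic use. With one term each, two site terms and one for arm, that is nine parameters for about 112 events (112/9 ≈ 12 per parameter).
- Fix the list before any analysis by arm and before database lock, and date the decision. If results by arm have already been seen, leave arm plus site as primary and name the list for the sensitivity analysis only.
- Use only values that reflect status before randomization. If that cannot be confirmed for medication, drop antiarrhythmic use.
- State a simple missing-covariate rule, for example single imputation or a missing indicator, so that every randomized participant stays in the model.
- Keep arm plus site as the sensitivity analysis.

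The cost is SAP wording and no new data. The small downsides are an HR conditional on the listed covariates and the need to settle the list and coding in advance.

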## **6.2 SECONDARY ENDPOINT ANALYSIS**

Prespecified secondary endpoints include atrial flutter and atrial fibrillation separately as incident outcomes, and adverse events before censorship including myocardial infarction, stroke or transient ischemic attack, heart failure exacerbation, emergency department visit, syncope, hospitalization, and death. Kaplan-Meier plots will be used to describe the survival distributions of secondary time-to-event outcomes (e.g., death) by trial arm and Cox hazard regression will be used for analysis. Continuous secondary endpoints will be described by randomization assignment using means and SDs, or medians and quartiles and categorical endpoints will be summarized using counts and percentages. Generalized linear models, which accommodate a range of outcome types including dichotomous, continuous, and counts, will be used for analysis. Randomization assignment will be included in all models, as well as study site used as a stratification factor in the randomization procedure. Additional models will adjust for the baseline patient characteristics in sensitivity analyses.

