#### 2.1.1 Study Visits and Windows

After screening and eligibility has been determined, participants will be enrolled and randomized at the baseline visit (date of cardioversion).

No in-person follow-up visits will be required. Phone call follow-ups will be conducted at week 1, month 1, month 3, and month 6 until first recurrence of AF or study completion (whichever comes first). This will be supplemented with chart review, including scanned medical records if the patient does not return for medical care, and analyses of ECG strips obtained from AliveCor (San Francisco, CA) KardiaMobile devices and Apple Watch (Cupertino, CA) devices already owned and in use by patients.

Table 1 outlines the window for each of the study visits. Clinical sites should make every possible effort to ensure that each study visit is conducted within the specified window.

[figure not shown]

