## 2.0 STUDY AIMS AND ENDPOINTS

*Hypothesis: Coffee abstinence will result in a lower recurrence of AF following cardioversion compared to continued caffeinated coffee consumption* (mention of coffee for the SAP refers to caffeinated coffee; those randomized to avoid coffee were indeed randomized to avoid all coffee).

Primary endpoint:

- The number of people with first confirmed clinical recurrence of AF or atrial flutter, or device-detected recurrence lasting longer than 30 seconds, following cardioversion in the coffee abstinence group compared to the continued caffeinated coffee consumption group analyzed as a time-to-event outcome.

Secondary endpoints:

- Adverse events before censorship, including myocardial infarction, stroke or transient ischemic attack, heart failure exacerbation, syncope, emergency department visit, hospitalization, and death

- Atrial flutter and atrial fibrillation separately as incident outcomes

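### SAP 6.2 lets adverse events other than death be compared without time at risk, and the documents disagree on when adverse-event follow-up ends

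*Combined protocol and SAP*

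**What the plan says.** **Endpoint.** SAP 2.0 lists "Adverse events before censorship, including myocardial infarction" and six further event types as a secondary endpoint. SAP 6.2 repeats the restriction: "adverse events before censorship including myocardial infarction, stroke or transient ischemic attack" and the rest. Neither section defines censoring for AEs.

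**Methods.** SAP 6.2 offers two routes. Kaplan-Meier plots serve "secondary time-to-event outcomes (e.g., death) by trial arm and Cox hazard regression will be used for analysis". For the other outcome types, "categorical endpoints will be summarized using counts and percentages" and "Generalized linear models, which accommodate a range of outcome types including dichotomous, continuous, and counts, will be used for analysis". On model terms it says "Randomization assignment will be included in all models, as well as study site". Baseline characteristics are added in sensitivity analyses. No offset or exposure term appears.

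**When follow-up ends.** Protocol 2.1.1 runs the phone calls "until first recurrence of AF or study completion (whichever comes first", and Table 2 schedules AE evaluation at those calls. Protocol 3.0 also ends the allocated intervention at recurrence. SAP 6.1 says: "Follow-up time for participants who do not experience the primary endpoint will be censored at the time of study withdrawal or end of study". It takes the sixth month as that end, and gives no censoring time for anyone who does recur. SAP 6.0, however, aims to collect secondary-endpoint data over the full six months for all randomized participants. Protocol 5.8 has site staff find AEs by reviewing medical records.

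**The concern.** If AE counting stops at first recurrence, the time in which a participant can have a counted AE is set by the primary outcome. The arm with more or earlier recurrences is then observed for less time. A percentage, a logistic model or a count model without an offset treats both arms as equally exposed. Emergency visits and hospitalizations are readily handled as yes/no or count outcomes, so an analyst following SAP 6.2 could take that route for them and still be within the plan.

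The safety comparison is at stake. With 100 participants per arm, readers will rely on the AE percentages and point estimates whether or not they reach significance. An arm could show fewer AEs only because it was watched for less time.

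**Working it through.** **Inputs from the documents.** 100 per arm; 50% recurrence without coffee and 10% loss (Protocol 10.1); hazard ratio (HR) 1.63 and two-sided 0.05 (Protocol 10.1, SAP 5.0); six months of follow-up.

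**Assumptions.** Exponential recurrence; AE counting stops at recurrence; the same true AE hazard in both arms; six-month AE risk of 5% to 30%, since the documents give no AE rate and no other AE figure.

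**1. The plan's own figure.** With exponential loss, the stated inputs give 112.6 events. Power = Φ(√112.6 × ln(1.63)/2 − 1.96) = Φ(0.63) = 73.6%, not 80%. The table in Protocol 10.1 places 1.63 in the row for 60% recurrence. There, 131.9 events give Φ(√131.9 × ln(1.63)/2 − 1.96) = Φ(0.85) = 80.1%. The 50% row with 10% loss shows 1.69. This mismatch is a separate matter, so both recurrence rates are carried below.

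**2. Mean time at risk.** Formula: (1 − exp(−6λ))/λ, ignoring loss.
- Abstinence: λ = ln2/6 = 0.1155 per month, giving 0.5/0.1155 = 4.33 months.
- Coffee: λ = 1.63 × 0.1155 = 0.1883, recurrence 67.7%, giving 0.677/0.1883 = 3.59 months.
- Ratio: 3.59/4.33 = 0.83.

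**3. Percentage with an AE before recurrence.** Formula: a/(a+λ) × (1 − exp(−6(a+λ))). For a 20% six-month AE risk, a = −ln(0.8)/6 = 0.0372.
- Abstinence: 0.0372/0.1527 × 0.600 = 14.6%.
- Coffee: 0.0372/0.2255 × 0.742 = 12.2%.
- Ratio: 0.84, with identical true hazards.

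| Assumed six-month AE risk | Abstinence | Coffee | Ratio | True AE HR that would be hidden |
|---|---|---|---|---|
| 5% | 3.62% | 3.01% | 0.83 | 1.21 |
| 10% | 7.26% | 6.05% | 0.83 | 1.21 |
| 20% | 14.61% | 12.23% | 0.84 | 1.22 |
| 30% | 22.08% | 18.57% | 0.84 | 1.23 |

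**4. The same data on person-time.** Mean time to first AE, recurrence or month 6 is 0.600/0.1527 = 3.93 months v 0.742/0.2255 = 3.29 months. The rates are 0.1461/3.93 and 0.1223/3.29, both 3.72 per 100 person-months, so the ratio is 1.00.

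**5. Sensitivity of the exposure ratio.** It is 0.79 at 60% recurrence (3.93 v 3.12 months) and 0.89 if 50% is the higher-recurrence arm (4.89 v 4.33 months). For Weibull recurrence with shapes 0.5 to 1.5 it runs from 0.77 to 0.87.

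**6. AEs brought on by recurrence.** Suppose a fraction q of recurrences brings a counted visit or admission. At 20% AE risk, 45.4% v 61.9% recur with no earlier AE, so the AE percentages become 14.6 + 45.4q v 12.2 + 61.9q. They are equal at q = 2.38/16.5, about 14% (about 16% at 60% recurrence). The ratio is 1.04 at q = 20% and 1.09 at q = 30%. The person-time ratio does not stay at 1 here either. At q = 20% it is (0.0372 + 0.2 × 0.1883)/(0.0372 + 0.2 × 0.1155) = 0.0749/0.0603 = 1.24.

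**7. Chance of a false significant result.** With 100 per arm and independent AEs, the differences in step 3 reach significance in that direction about 5%, 7% and 9% of the time at AE risks of 10%, 20% and 30%.

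**The case against.** The strongest reply is that the SAP is silent here and has not chosen a wrong method. Its Cox sentence comes just before the percentages, its example (death) is itself a listed AE, and the example is not exclusive. The generalized linear model sentence reads as generic text: it covers continuous outcomes, and no listed secondary endpoint is continuous. SAP 6.0 and Protocol 5.8 allow AE capture to month 6, in which case the dependence on recurrence goes away. The effect is also modest, at 2.4 participants per 100 for a 20% AE risk, on endpoints that Protocol 2.2 calls exploratory.

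Much of this stands. A reader might infer that the SAP prescribes percentages and models without an offset for all AEs, and that the arm with more recurrences will look safer. The documents support neither inference. No AE is expressly sent to that route. The direction requires a real recurrence difference, counting that stops at recurrence, and AEs unrelated to recurrence; step 6 shows how the last can fail.

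The gap remains, however. Collecting data to six months does not widen an endpoint limited to events before censoring. One of the two permitted routes ignores time at risk, and the choice is left open. The low chance of a false significant result does not help, because the problem lies in the estimate.

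**Conclusion.** The point holds as a conditional one. SAP 6.2 permits an AE comparison that ignores time at risk, and the documents do not settle whether AE counting ends at recurrence. If it does, at 50% recurrence and HR 1.63 the arms differ by about 17% in mean time at risk. Equal true AE hazards then appear as a percentage ratio of 0.83 to 0.84, which could hide a true AE hazard ratio of about 1.21 to 1.23. These figures rest on exponential recurrence, AEs independent of recurrence, and AE risks that are assumed. The raw comparison can mislead in either direction: it favours the arm with more recurrences when AEs are independent, and can reverse when recurrences bring counted visits or admissions. If AEs are captured to month 6 for everyone, this mechanism largely disappears. The matter should be settled in the SAP; it does not touch the primary analysis.

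**What to change.** In SAP 6.2:
- Analyse every AE type on a time-at-risk basis: Cox for time to first event or, for counts, a Poisson or negative-binomial model with log observed follow-up as offset.
- Report events per 100 person-months by arm beside the counts and percentages.
- Define censoring for AEs, and reconcile Protocol 2.1.1 with SAP 6.0, 6.1 and 6.2 on when AE follow-up ends.
- State whether an event on the recurrence date counts. Step 6 shows that this can move the result whichever model is used.

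The cost is SAP wording and slightly more analysis, using event and follow-up dates. The limits should be stated too: neither Cox nor an offset recovers events after recurrence, and neither removes informative censoring if recurrence and AE risk are linked.
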